11.0 STUDY MANAGEMENT

11.1 Conflict of Interest

Any investigator who has a conflict of interest with this study (patent ownership, royalties, or financial gain greater than the minimum allowable by their institution, etc.) must have the conflict reviewed by their own institution's COI committee. All investigators will follow the University conflict of interest policy.

11.2 Institutional Review Board (IRB) Approval and Consent

It is expected that the IRB will have the proper representation and function in accordance with federally mandated regulations. The IRB should approve the consent form and protocol.

In obtaining and documenting informed consent, the investigator should comply with the applicable regulatory requirement(s), and should adhere to Good Clinical Practice (GCP) and to ethical principles that have their origin in the Declaration of Helsinki.

Before recruitment and enrollment onto this study, the patient will be given a full explanation of the study and will be given the opportunity to review the consent form. Each consent form must include all the relevant elements currently required by the FDA Regulations and local or state regulations. Once this essential information has been provided to the patient and the investigator is assured that the patient understands the implications of participating in the study, the patient will be asked to give consent to participate in the study by signing an IRB-approved consent form.

Prior to a patient's participation in the trial, the written informed consent form should be signed and personally dated by the patient and by the person who conducted the informed consent discussion.

11.2 Data Completion

11.2.1 OnCore Data Entry

Data, as indicated by Sponsor, will be entered into OnCore – UC Irvine's Clinical Trial Management system. The Investigator is responsible for ensuring all entries are accurate and correct. The Investigator must maintain accurate source data that support OnCore data entry. All data will be entered as per Sponsor's specification and timeframe.

11.2.2 Recording of Events

CONFIDENTIAL

This material is the property of the [UC Irvine Chao Family Comprehensive Cancer Center](#). Do not disclose or use except as authorized in writing by the study sponsor.

All investigator initiated treatment trials require that adverse events, serious adverse events, deviations, and unanticipated problems be entered into the clinical trial management system (CTMS), OnCore. All entries must be entered in OnCore within the timelines specified in section 7.4-7.6 of being aware of the adverse event, serious adverse event, violation, deviation, or unanticipated problem. Adverse events and violations/deviations and adverse events that are unanticipated problems that require prompt reporting to the DSMB must be entered into OnCore according to the timelines as specified in section 7.3-7.5

11.3 Data and Safety Monitoring/Auditing

11.3.1 Quality Assurance

Quality assurance activities will be conducted as per UC Irvine Chao Family Comprehensive Cancer Center's Quality Assurance Monitoring and Auditing Plan and at the discretion of the CFCCC Data and Safety Monitoring Board in order to ensure patient safety and data integrity oversight. By conducting internal monitoring and auditing, the CFCCC will ensure compliance with high quality standards and all applicable regulations, guidelines, and institutional policies. Trial monitoring and auditing may be completed remotely or on-site by the Quality Assurance Officer. Participating sites may follow their own internal quality assurance policies in order to maintain patient safety and data integrity oversight. The investigator must permit study-related monitoring/auditing and provide access to study-related materials.

11.3.2 Data and Safety Monitoring Plan

This is a risk level 2 study, as defined in the Chao Family Comprehensive Cancer Center (CFCCC) Data and Safety Monitoring Plan (DSMP) because it is a study in which the IND is exempt by the FDA.

The Principal Investigator (PI), co-investigator, clinical research coordinator, and statistician are responsible for monitoring of data and safety for this study. For studies that have stopping rules for safety and efficacy, the PI will be responsible for the implementation and make changes as applicable. The CFCCC Data and Safety Monitoring Board (DSMB) is an independent body responsible for the safety of study subjects as well as the data integrity of the protocol. Data and safety will be reported to the DSMB with submission of progress reports that include aggregated reports of adverse events, serious adverse events, deviations, and violations. In addition, all adverse events, deviations, and violations will be reported promptly to the DSMB for review according to section 7.4 and section 7.5.

11.4 Protocol Deviation

All protocol deviations will be reported in accordance with UCI IRB, UCI CFCCC Stern Center policies and the participating site's IRB policies.

11.5 Amendments to the Protocol

Should amendments to the protocol be required, the amendments will be originated and documented by the Principal Investigator. It should also be noted that when an amendment to the protocol substantially alters the study design or the potential risk to the patient, a revised consent form might be required.

CONFIDENTIAL

This material is the property of the [UC Irvine Chao Family Comprehensive Cancer Center](#). Do not disclose or use except as authorized in writing by the study sponsor.

The written amendment, and if required the amended consent form, must be sent to the IRB for approval prior to implementation.

11.6 Record Retention

Study documentation includes all Case Report Forms, data correction forms or queries, source documents, Sponsor-Investigator correspondence, monitoring logs/letters, and regulatory documents (e.g., protocol and amendments, IRB correspondence and approval, signed patient consent forms).

Source documents include all recordings of observations or notations of clinical activities and all reports and records necessary for the evaluation and reconstruction of the clinical research study.

Government agency regulations and directives require that the study investigator must retain all study documentation pertaining to the conduct of a clinical trial. In the case of a study with a drug seeking regulatory approval and marketing, these documents shall be retained for at least two years after the last approval of marketing application in an International Conference on Harmonization (ICH) region. In all other cases, study documents should be kept on file until three years after the completion and final study report of this investigational study.

11.7 Obligations of Investigators

The Principal Investigator is responsible for the conduct of the clinical trial at the site in accordance with Title 21 of the Code of Federal Regulations and/or the Declaration of Helsinki. The Principal Investigator is responsible for personally overseeing the treatment of all study patients. The Principal Investigator must assure that all study site personnel, including sub-investigators and other study staff members, adhere to the study protocol and all FDA/GCP/NCI regulations and guidelines regarding clinical trials both during and after study completion.

The Principal Investigator at each institution or site will be responsible for assuring that all the required data will be collected and entered onto the Case Report Forms. Periodically, monitoring visits will be conducted and the Principal Investigator will provide access to his/her original records to permit verification of proper entry of data. At the completion of the study, all case report forms will be reviewed by the Principal Investigator and will require his/her final signature to verify the accuracy of the data.

13.0 APPENDICES

APPENDIX A: ECOG Performance Status Criteria

ECOG Performance Status Scale		Karnofsky Performance Scale	
Grade	Descriptions	Percent	Description
0	Normal activity. Fully active, able to carry on all pre-disease performance without restriction.	100	Normal, no complaints, no evidence of disease.
		90	Able to carry on normal activity; minor signs or symptoms of disease.
1	Symptoms, but ambulatory. Restricted in physically strenuous activity, but ambulatory and able to carry out work of a light or sedentary nature (e.g., light housework, office work).	80	Normal activity with effort; some signs or symptoms of disease.
		70	Cares for self, unable to carry on normal activity or to do active work.
2	In bed <50% of the time. Ambulatory and capable of all self-care, but unable to carry out any work activities. Up and about more than 50% of waking hours.	60	Requires occasional assistance, but is able to care for most of his/her needs.
		50	Requires considerable assistance and frequent medical care.
3	In bed >50% of the time. Capable of only limited self-care, confined to bed or chair more than 50% of waking hours.	40	Disabled, requires special care and assistance.
		30	Severely disabled, hospitalization indicated. Death not imminent.
4	100% bedridden. Completely disabled. Cannot carry on any self-care. Totally confined to bed or chair.	20	Very sick, hospitalization indicated. Death not imminent.
		10	Moribund, fatal processes progressing rapidly.

CONFIDENTIAL

This material is the property of the [UC Irvine Chao Family Comprehensive Cancer Center](#). Do not disclose or use except as authorized in writing by the study sponsor.

5	Dead.	0	Dead.
---	-------	---	-------

APPENDIX B: Liver Safety: Suggested Actions and Follow-up Assessments

Selected tests may be obtained in the event of a treatment-emergent hepatic abnormality and may be required in follow-up with patients in consultation with the principal investigator.

Hepatic Monitoring Tests

Hepatic Hematology

Hemoglobin (HGB)

Hematocrit (HCT)

Erythrocytes (RBC)

Leukocytes (WBC)

Neutrophils

Lymphocytes

Monocytes

Eosinophils

Basophils

Platelets (PLT)

Haptoglobin

Hepatic Coagulation

Prothrombin Time (PT)

Prothrombin Time, INR

Hepatic Serologies

Hepatitis A antibody, total

Hepatitis A antibody, IgM

Hepatitis B surface antigen

Hepatitis B surface antibody

Hepatitis B Core antibody

Hepatitis C antibody

Hepatitis E antibody, IgG

Hepatitis E antibody, IgM

Hepatic Chemistry

Total bilirubin

Direct bilirubin

Alkaline phosphatase

Alanine aminotransferase (ALT)

Aspartate aminotransferase (AST)

Gamma-glutamyl transferase (GGT)

Creatine phosphokinase (CPK)

Recommended Autoimmune Serology

Anti-nuclear antibody

Anti-smooth muscle antibody

Anti-actin antibody

APPENDIX C: Inducers and Strong Inhibitors of CYP3A

The information in this appendix is provided for guidance to investigators and does not preclude the use of these medications if clinically indicated

Strong Inducers of CYP3A

Carbamazepine

Rifapentine

Dexamethasone

Rifabutin

Phenobarbital/phenobarbitone

Rifampin

Phenytoin

St. John's Wort

Moderate Inducers of CYP3A

Bosentan

Primidone

Lenisurad

Telostristat ethyl

Modafinil

Strong Inhibitors of CYP3A

Aprepitant

Itraconazole

CONFIDENTIAL

This material is the property of the UC Irvine Chao Family Comprehensive Cancer Center. Do not disclose or use except as authorized in writing by the study sponsor.

Ciprofloxacin	Ketoconazole
Clarithromycin	Nefazodone
Conivaptan	Posaconazole
Diltiazem	Troleandomycin
Erythromycin	Verapamil
Fluconazole	

APPENDIX D: Pill Diaries

Pill Diary Cycle 1

UCI 18-79 Abemaciclib Pill Diary		Cycle: 1
Subject Initials: _____	Subject ID: _____	Current Total Dosage: _____
Dosing Instructions: Abemaciclib will be taken twice a day, once in the morning and once in the evening. If you forget to take a dose, do not make up the dose and record that the dose was skipped. Please record the date and times you take the Abemaciclib. Please remember to bring your bottles and Pill Diary to each clinic visit. If you experience any symptoms, please do not take the dose and contact the Study Team.		
Treating Investigator: _____		Next Clinic Visit: _____
Nurse Navigator: _____		Study Coordinator: _____

Day 1 (Same day as 500mg Fulvestrant Injection)		Date: _____
Dose taken in the morning:	_____ mg	Time of morning dose: _____
Dose taken in the evening:	_____ mg	Time of evening dose: _____
Comments:		
Day 2		Date: _____
Dose taken in the morning:	_____ mg	Time of morning dose: _____
Dose taken in the evening:	_____ mg	Time of evening dose: _____
Comments:		
Day 3		Date: _____
Dose taken in the morning:	_____ mg	Time of morning dose: _____
Dose taken in the evening:	_____ mg	Time of evening dose: _____
Comments:		
Day 4		Date: _____

CONFIDENTIAL

This material is the property of the [UC Irvine Chao Family Comprehensive Cancer Center](#). Do not disclose or use except as authorized in writing by the study sponsor.

Protocol #: UCI 18-79
MP 09/09/2020

Dose taken in the morning:	_____ mg	Time of morning dose: _____
Dose taken in the evening:	_____ mg	Time of evening dose: _____
Comments:		
Day 5		Date: _____
Dose taken in the morning:	_____ mg	Time of morning dose: _____
Dose taken in the evening:	_____ mg	Time of evening dose: _____
Comments:		
Day 6		Date: _____
Dose taken in the morning:	_____ mg	Time of morning dose: _____
Dose taken in the evening:	_____ mg	Time of evening dose: _____
Comments:		
Day 7		Date: _____
Dose taken in the morning:	_____ mg	Time of morning dose: _____
Dose taken in the evening:	_____ mg	Time of evening dose: _____
Comments:		
Day 8		Date: _____
Dose taken in the morning:	_____ mg	Time of morning dose: _____
Dose taken in the evening:	_____ mg	Time of evening dose: _____
Comments:		
Day 9		Date: _____
Dose taken in the morning:	_____ mg	Time of morning dose: _____
Dose taken in the evening:	_____ mg	Time of evening dose: _____
Comments:		
Day 10		Date: _____
Dose taken in the morning:	_____ mg	Time of morning dose: _____
Dose taken in the evening:	_____ mg	Time of evening dose: _____
Comments:		
Day 11		Date: _____

CONFIDENTIAL

This material is the property of the [UC Irvine Chao Family Comprehensive Cancer Center](#). Do not disclose or use except as authorized in writing by the study sponsor.

Protocol #: UCI 18-79
MP 09/09/2020

Dose taken in the morning:	_____ mg	Time of morning dose: _____
Dose taken in the evening:	_____ mg	Time of evening dose: _____
Comments:		
Day 12		Date: _____
Dose taken in the morning:	_____ mg	Time of morning dose: _____
Dose taken in the evening:	_____ mg	Time of evening dose: _____
Comments:		
Day 13		Date: _____
Dose taken in the morning:	_____ mg	Time of morning dose: _____
Dose taken in the evening:	_____ mg	Time of evening dose: _____
Comments:		
Day 14		Date: _____
Dose taken in the morning:	_____ mg	Time of morning dose: _____
Dose taken in the evening:	_____ mg	Time of evening dose: _____
Comments:		
Day 15 (same day as 500mg Fulvestrant injection)		Date: _____
Dose taken in the morning:	_____ mg	Time of morning dose: _____
Dose taken in the evening:	_____ mg	Time of evening dose: _____
Comments:		
Day 16		Date: _____
Dose taken in the morning:	_____ mg	Time of morning dose: _____
Dose taken in the evening:	_____ mg	Time of evening dose: _____
Comments:		
Day 17		Date: _____
Dose taken in the morning:	_____ mg	Time of morning dose: _____
Dose taken in the evening:	_____ mg	Time of evening dose: _____
Comments:		
Day 18		Date: _____

CONFIDENTIAL

This material is the property of the [UC Irvine Chao Family Comprehensive Cancer Center](#). Do not disclose or use except as authorized in writing by the study sponsor.

Protocol #: UCI 18-79
MP 09/09/2020

Dose taken in the morning:	_____ mg	Time of morning dose: _____
Dose taken in the evening:	_____ mg	Time of evening dose: _____
Comments:		
Day 19		Date: _____
Dose taken in the morning:	_____ mg	Time of morning dose: _____
Dose taken in the evening:	_____ mg	Time of evening dose: _____
Comments:		
Day 20		Date: _____
Dose taken in the morning:	_____ mg	Time of morning dose: _____
Dose taken in the evening:	_____ mg	Time of evening dose: _____
Comments:		
Day 21		Date: _____
Dose taken in the morning:	_____ mg	Time of morning dose: _____
Dose taken in the evening:	_____ mg	Time of evening dose: _____
Comments:		
Day 22		Date: _____
Dose taken in the morning:	_____ mg	Time of morning dose: _____
Dose taken in the evening:	_____ mg	Time of evening dose: _____
Comments:		

Pill Diary Cycle 2 and Forward

CONFIDENTIAL

This material is the property of the [UC Irvine Chao Family Comprehensive Cancer Center](#). Do not disclose or use except as authorized in writing by the study sponsor.

UCI 18-79 Abemaciclib Pill Diary		Cycle: _____
Subject Initials: _____ Subject ID: _____ Current Total Dosage: _____		
Dosing Instructions: Abemaciclib will be taken twice a day, once in the morning and once in the evening. If you forget to take a dose, do not make up the dose and record that the dose was skipped. Please record the date and times you take the Abemaciclib. Please remember to bring your bottles and Pill Diary to each clinic visit. If you experience any symptoms, please do not take the dose and contact the Study Team.		
Treating Investigator: _____		Next Clinic Visit: _____
Nurse Navigator: _____		
Study Coordinator: _____		

Day 1 (Same day as 500mg Fulvestrant Injection)		Date: _____
Dose taken in the morning:	_____ mg	Time of morning dose: _____
Dose taken in the evening:	_____ mg	Time of evening dose: _____
Comments:		
Day 2		Date: _____
Dose taken in the morning:	_____ mg	Time of morning dose: _____
Dose taken in the evening:	_____ mg	Time of evening dose: _____
Comments:		
Day 3		Date: _____
Dose taken in the morning:	_____ mg	Time of morning dose: _____
Dose taken in the evening:	_____ mg	Time of evening dose: _____
Comments:		
Day 4		Date: _____
Dose taken in the morning:	_____ mg	Time of morning dose: _____
Dose taken in the evening:	_____ mg	Time of evening dose: _____
Comments:		
Day 5		Date: _____
Dose taken in the morning:	_____ mg	Time of morning dose: _____
Dose taken in the evening:	_____ mg	Time of evening dose: _____

CONFIDENTIAL

This material is the property of the [UC Irvine Chao Family Comprehensive Cancer Center](#). Do not disclose or use except as authorized in writing by the study sponsor.

Protocol #: UCI 18-79
MP 09/09/2020

Comments:		
Day 6		Date: _____
Dose taken in the morning:	_____ mg	Time of morning dose: _____
Dose taken in the evening:	_____ mg	Time of evening dose: _____
Comments:		
Day 7		Date: _____
Dose taken in the morning:	_____ mg	Time of morning dose: _____
Dose taken in the evening:	_____ mg	Time of evening dose: _____
Comments:		
Day 8		Date: _____
Dose taken in the morning:	_____ mg	Time of morning dose: _____
Dose taken in the evening:	_____ mg	Time of evening dose: _____
Comments:		
Day 9		Date: _____
Dose taken in the morning:	_____ mg	Time of morning dose: _____
Dose taken in the evening:	_____ mg	Time of evening dose: _____
Comments:		
Day 10		Date: _____
Dose taken in the morning:	_____ mg	Time of morning dose: _____
Dose taken in the evening:	_____ mg	Time of evening dose: _____
Comments:		
Day 11		Date: _____
Dose taken in the morning:	_____ mg	Time of morning dose: _____
Dose taken in the evening:	_____ mg	Time of evening dose: _____
Comments:		
Day 12		Date: _____
Dose taken in the morning:	_____ mg	Time of morning dose: _____
Dose taken in the evening:	_____ mg	Time of evening dose: _____
Comments:		

CONFIDENTIAL

This material is the property of the [UC Irvine Chao Family Comprehensive Cancer Center](#). Do not disclose or use except as authorized in writing by the study sponsor.

Day 13		Date: _____
Dose taken in the morning:	_____ mg	Time of morning dose: _____
Dose taken in the evening:	_____ mg	Time of evening dose: _____
Comments:		
Day 14		Date: _____
Dose taken in the morning:	_____ mg	Time of morning dose: _____
Dose taken in the evening:	_____ mg	Time of evening dose: _____
Comments:		
Day 15		Date: _____
Dose taken in the morning:	_____ mg	Time of morning dose: _____
Dose taken in the evening:	_____ mg	Time of evening dose: _____
Comments:		
Day 16		Date: _____
Dose taken in the morning:	_____ mg	Time of morning dose: _____
Dose taken in the evening:	_____ mg	Time of evening dose: _____
Comments:		
Day 17		Date: _____
Dose taken in the morning:	_____ mg	Time of morning dose: _____
Dose taken in the evening:	_____ mg	Time of evening dose: _____
Comments:		
Day 18		Date: _____
Dose taken in the morning:	_____ mg	Time of morning dose: _____
Dose taken in the evening:	_____ mg	Time of evening dose: _____
Comments:		
Day 19		Date: _____
Dose taken in the morning:	_____ mg	Time of morning dose: _____
Dose taken in the evening:	_____ mg	Time of evening dose: _____
Comments:		
Day 20		Date: _____

CONFIDENTIAL

This material is the property of the [UC Irvine Chao Family Comprehensive Cancer Center](#). Do not disclose or use except as authorized in writing by the study sponsor.

Dose taken in the morning:	_____ mg	Time of morning dose: _____
Dose taken in the evening:	_____ mg	Time of evening dose: _____
Comments:		
Day 21		Date: _____
Dose taken in the morning:	_____ mg	Time of morning dose: _____
Dose taken in the evening:	_____ mg	Time of evening dose: _____
Comments:		
Day 22		Date: _____
Dose taken in the morning:	_____ mg	Time of morning dose: _____
Dose taken in the evening:	_____ mg	Time of evening dose: _____
Comments:		

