Grade 1 ($>ULN-3.0 \times ULN$), Grade 2 ($>3.0-5.0 \times ULN$), WITHOUT increase in total bilirubin above $2 \times ULN$	No dose modification required
Persistent or Recurrent Grade 2, or Grade 3 ($>5.0-20.0 \times ULN$), WITHOUT increase in total bilirubin above $2 \times ULN$	Suspend dose until toxicity resolves to baseline or Grade 1. Resume at next lower dose.
Elevation in AST and/or ALT $>3 \times ULN$ WITH total bilirubin $>2 \times ULN$, in the absence of cholestasis	Discontinue abemaciclib
Grade 4 ($>20.0 \times ULN$)	Discontinue abemaciclib

Details for hepatic monitoring depend upon the severity and persistence of observed laboratory test abnormalities. If a study patient experiences elevated ALT $5 \times ULN$ and elevated TBL $2 \times ULN$, or ALT $8 \times ULN$, liver tests, including ALT, AST, TBL, direct bilirubin, gamma-glutamyl transferase (GGT), and creatine phosphokinase (CPK), should be repeated within 3 to 5 days to confirm the abnormality and to determine if it is increasing or decreasing. If the abnormality persists or worsens, clinical and laboratory monitoring should be initiated by the investigator, based on the hepatic monitoring tests below in Appendix B.

Diarrhea

At enrollment, patients should receive instructions on the prompt management of diarrhea. In the event of diarrhea, supportive care measures should be initiated as early as possible. These include the following:

CONFIDENTIAL

This material is the property of the [UC Irvine Chao Family Comprehensive Cancer Center](#). Do not disclose or use except as authorized in writing by the study sponsor.

- At the first sign of loose stools, the patient should initiate antidiarrheal therapy (e.g. loperamide) and notify the investigator for further instructions and appropriate follow up.
- Patients should also be encouraged to drink fluids (e.g., 8 to 10 glasses of clear liquids per day).
- Site personnel should assess response within 24 hours.
- Refer to table below for additional information for diarrhea management and dose modification.

Diarrhea Dose Management Guidelines	
At the first sign of loose stools, start treatment with antidiarrheal agents, such as loperamide.	
CTCAE Grade	Action
Grade 1	No dose modification required
Grade 2	If toxicity does not resolve within 24 hours to ≤ Grade 1, suspend dose until resolution. No dose reduction is required.

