Persistent or recurrent Grade 2 toxicity that does not resolve with maximal supportive measures within 7 days to baseline or Grade 1	Suspend dose until toxicity resolves to baseline or ≤Grade 1. Resume at next lower dose.
Grade 3-4	

Note: Abemaciclib has been shown to increase serum creatinine due to inhibition of renal tubular transporters without affecting glomerular function (as measured by iohexol clearance). In clinical studies, increases in serum creatinine occurred within the first month of abemaciclib dosing, remained elevated but stable through the treatment period, were reversible upon treatment discontinuation, and were not accompanied by changes in markers of renal function, such as blood urea nitrogen (BUN), cystatin C, or calculated glomerular filtration rate based on cystatin C.

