4.2.2 Dose Suspension and Cycle Delays

Both dose suspension (within a cycle) and cycle delay are permitted. Study treatment may be held up to 14 days within a cycle or at start of next cycle to permit sufficient time for recovery from the toxicity. Patients not recovering from toxicity within 14 days should be considered for discontinuation at the discretion of the investigator. In exceptional circumstances, a delay >14 days is permitted upon agreement with the principal investigator (PI).

A delay of a cycle due to holiday, weekend, bad weather, or other unforeseen circumstances will be permitted for a maximum of 7 days and not counted as a protocol deviation. In exceptional circumstances, a delay >7 days is permitted upon agreement with PI.

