4.3.2 Supportive Management for Diarrhea in Patients Receiving Abemaciclib

Patients should receive instructions on the management of diarrhea. In the event of diarrhea, supportive measures should be initiated as early as possible. These include the following:

- At the first sign of loose stools, the patient should initiate anti-diarrheal therapy (e.g., loperamide) and notify the investigator for further instructions and appropriate follow-up.
- Patients should also be encouraged to drink fluids (e.g., 8 to 10 glasses of clear liquids per day).
- Site personnel should assess response within 24 hours.
- If diarrhea does not resolve with anti-diarrheal therapy within 24 hours to at least Grade 1 (per CTCAE v 5.0), study abemaciclib treatment should be suspended until diarrhea is resolved to at least Grade 1.
- When abemaciclib treatment recommences, dosing should be adjusted as outlined in Section 4.2.1. In severe cases of diarrhea, the measuring of

CONFIDENTIAL

This material is the property of the [UC Irvine Chao Family Comprehensive Cancer Center](#). Do not disclose or use except as authorized in writing by the study sponsor.

neutrophil counts and body temperature and proactive management of diarrhea with antidiarrheal agents should be considered.

If diarrhea is severe (requiring intravenous rehydration) and/or associated with fever or severe neutropenia, broad-spectrum antibiotics such as fluoroquinolones should be considered. Patients with severe diarrhea or any diarrhea associated with severe nausea or vomiting should be carefully monitored and given intravenous fluid and electrolyte replacement as clinically indicated.

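### Both pill diaries tell patients to withhold abemaciclib for any symptom, while section 4.2.1 requires no dose change for Grade 1 diarrhea and most other Grade 1-2 non-hematologic toxicity

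*Combined protocol and SAP*

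**What the plan says.** The dosing instructions in both Appendix D diaries (Cycle 1, and Cycle 2 and Forward) contain the same sentence: "If you experience any symptoms, please do not take the dose and contact the Study Team". It names no grade, severity or suspected cause, and the diaries do not mention loperamide.

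Section 4.2.1 works by grade:

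- Grade 1 diarrhea: "No dose modification required".
- Grade 2 diarrhea: "If toxicity does not resolve within 24 hours to ≤ Grade 1, suspend dose until resolution". A further row also suspends Grade 2 diarrhea that persists, or that returns once the same dose has been resumed, despite maximal supportive care.
- Other non-hematologic toxicity at Grade 1-2: again no modification required. The exception is "Persistent or recurrent Grade 2 toxicity that does not resolve with maximal supportive measures within 7 days to baseline or Grade 1", which leads to suspension and the next lower dose.

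For loose stools, the patient-level instruction in 4.2.1 is that "the patient should initiate antidiarrheal therapy (e.g. loperamide) and notify the investigator for further instructions", followed by "Site personnel should assess response within 24 hours". The later section on supportive management for diarrhea (numbered 4.3.2, after 4.4.1) repeats this and suspends abemaciclib under the condition "If diarrhea does not resolve with anti-diarrheal therapy within 24 hours to at least Grade 1".

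Two other sections bear on the point. Section 4.2.2 says "Both dose suspension (within a cycle) and cycle delay are permitted". Section 8.3 says that missed or held doses are not made up, and that compliance is judged from the diary and the returned drug.

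**The concern.** The diary is the dosing document the patient has at home. Its rule is to hold at the onset of any symptom. The rule in 4.2.1 is to continue through mild toxicity and to suspend on defined criteria. For mild events the two give opposite defaults.

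This will come up in routine treatment. Section 8.1 lists diarrhea, nausea, abdominal pain and fatigue among the common effects of abemaciclib. Because the diary does not limit the symptom to a suspected abemaciclib effect, hot flashes on fulvestrant (23.5% in section 8.2, from second-line use) fall under it too if it is read literally.

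What is at stake is dose intensity and clean compliance data. A patient who follows the diary skips doses that the dosing rules would have given. One who continues, as 4.2.1 allows, departs from the diary. The diary also leaves out the step that the body text puts first for loose stools, which is prompt antidiarrheal treatment.

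**Working it through.** The plan states no figure for doses lost, so there is nothing to reproduce. The check is a comparison of the rules and a dose count.

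**Inputs.** 150 mg twice daily and a 28-day cycle (section 4.1.1); held doses not made up (section 8.3); grade rules (section 4.2.1); hold at any symptom until the team is reached (Appendix D).

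**Doses per cycle.** 2 × 28 = 56 doses; 56 × 150 mg = 8,400 mg. One dose is 1/56 = 1.8% of the cycle.

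**Rules side by side.**

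| Event | Section 4.2.1 | Diary |
|---|---|---|
| Grade 1 diarrhea | continue | hold and call |
| Grade 2 diarrhea, first 24 hours | continue while awaiting resolution | hold and call |
| Grade 2 diarrhea, not down to Grade 1 after 24 hours | suspend | hold and call |
| Grade 2 diarrhea persisting or recurring after resuming the same dose, despite maximal support | suspend | hold and call |
| Other non-hematologic Grade 1-2 | continue, unless Grade 2 is persistent or recurrent | hold and call |

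The conflict lies in the first, second and last rows. In the third and fourth rows both instructions withhold the drug.

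**Doses lost through the diary hold.** Doses lost = number of scheduled dose times that pass before the team clears the patient. With doses 12 hours apart:

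- cleared before the next dose: 0 of 56;
- 12 hours of missed dosing: 1 of 56 = 1.8% (150 mg);
- 24 hours: 2 of 56 = 3.6% (300 mg);
- 48 hours: 4 of 56 = 7.1%;
- 72 hours: 6 of 56 = 10.7%.

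The hold lengths are assumptions that show the range, because the documents give no call-back time for any symptom. Under 4.2.1 the corresponding loss for Grade 1 diarrhea is 0. For a first Grade 2 episode that does not resolve, the two rules differ by at most the 2 doses that fall in the 24 hours before 4.2.1 itself suspends.

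**What cannot be computed.** The documents give no symptom rate for this combination in this setting and no dose-response relation, so neither a number of affected patients nor a change in pCR follows. The Simon two-stage calculation in section 10.2 does not depend on this point.

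**The case against.** The best defense is that the diary asks only for a precautionary pause. The same sentence sends the patient to the study team, who can restart her at once. A table entry saying that no modification is required does not forbid a short hold, and 4.2.2 permits suspension within a cycle. That section allows treatment to be held for up to 14 days, which is 14 × 2 = 28 doses, so a dose or two is small beside what the protocol already tolerates. Over-holding also errs toward safety and prompts contact. All of this is fair, and it limits the size of the point. It does not remove it: 4.2.2 allows holds for recovery from toxicity and does not replace the grade rules, and the pause still withholds doses that those rules would continue.

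Three stronger readings are tempting, and the documents do not support them.

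- A reader might infer that each mild diarrhea episode costs one to two doses, taking the 24-hour site check as the end of the hold. In context that check assesses response to antidiarrheal treatment and sets no limit on a hold. The loss can be zero, or more than two.
- A reader might infer that failure to resolve within 24 hours is the only reason to suspend for Grade 2 diarrhea. The row on persistent or recurrent Grade 2 is a second one.
- A reader might infer that the diary will produce different dosing in different patients. All patients receive the same diary, so this needs some of them to ignore it, or to follow the separate diarrhea instructions given at enrollment. That is possible, but not shown.

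**Conclusion.** The conflict is real and appears in both diaries. A patient who follows the diary can lose doses that 4.2.1 would give for mild, common symptoms, and those doses are not recovered. Each episode costs nothing if the team clears her before the next dose, and 1.8% of a cycle for each 12 hours beyond that, with no documented ceiling. This rests on full-dose twice-daily treatment and on the patient taking the diary literally.

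It is a contradiction in patient-facing dosing instructions with a modest effect on dose intensity. It does not touch the sample size or the error rates, and a reader should not infer that it lowers pCR: treatment has no fixed length (section 4.5) and the documents offer no basis for such a figure. It should be corrected, because the events are common and the remedy is one sentence.

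**What to change.** Replace the sentence in both Appendix D diaries with:

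> For mild symptoms, keep taking abemaciclib and call the study team the same day; for loose stools, start loperamide at once. If a symptom is severe, if diarrhea is not back to mild within 24 hours, if more than mild diarrhea returns after you restarted, or if you have new or worse cough or breathlessness, do not take the next dose until the study team tells you what to do.

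The investigator should confirm the hold triggers against 4.2.1 before the text is used. The cough and breathlessness trigger is deliberately stricter than the table, which requires no change for Grade 1-2 ILD/pneumonitis: a patient cannot grade possible ILD at home, and Grade 3-4 means discontinuation.

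The cost is a small written amendment with IRB approval before use (section 11.5), with no new visits or procedures. The drawback is that patients must judge what counts as mild; the same-day call limits that risk.
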